4.3.3 Investigational Medicinal Product Accountability

Taselisib and placebo will be supplied by the Sponsor in all participating countries. Fulvestrant will be supplied by the Sponsor in all participating countries except the countries where procurement will be reimbursed. The study site will acknowledge receipt of Sponsor-supplied study drugs using the IxRS to confirm the shipment condition and content. Any damaged shipments will be replaced.

Sponsor-supplied study drugs will either be disposed of at the study site according to the study site's institutional standard operating procedure or returned to the Sponsor with the appropriate documentation. The Sponsor must agree with the method of destruction at each investigational site. The site must obtain written authorization from the Sponsor before any Sponsor-supplied medication is destroyed, and destruction must be documented on the appropriate form.

Accurate records of all Sponsor-supplied medications received at, dispensed from, returned to, and disposed of by the study site should be recorded on the Drug Inventory Log.

4.3.4 Post-Study Access to Taselisib

Currently, the Sponsor does not have any plans to provide taselisib or any other study treatments or interventions after the end of the study or for any patient who has discontinued or withdrawn from the study. Crossover from the control arm to the taselisib arm is not allowed. The Sponsor will evaluate whether to continue providing taselisib after the main study is over in accordance with the Roche Global Policy on Continued Access to Investigational Medicinal Product.

In the event that the Sponsor deems post-trial access to taselisib to be appropriate, the Sponsor may offer post-trial access to the study drug (taselisib) free of charge to eligible patients in accordance with the Roche Global Policy on Continued Access to Investigational Medicinal Product, as outlined below.

A patient will be eligible to receive study drug after the end of the study if all of the following conditions are met:

- The patient has a life-threatening or severe medical condition and requires continued study drug treatment for his or her well-being.
- There are no appropriate alternative treatments available to the patient.
- The patient and his or her doctor comply with and satisfy any legal or regulatory requirements that apply to them.

A patient will not be eligible to receive study drug after the end of the study if any of the following conditions are met:

- The study drug is commercially marketed in the patient's country and is reasonably accessible to the patient (e.g., is covered by the patient's insurance or wouldn't otherwise create a financial hardship for the patient).
- The Sponsor has discontinued development of the study drug or data suggest that the study drug is not effective for ER+, HER2-negative MBC.
- The Sponsor has reasonable safety concerns regarding the study drug as treatment for ER+, HER2-negative MBC.
- Provision of study drug is not permitted under the laws and regulations of the patient's country.

The Roche Global Policy on Continued Access to Investigational Medicinal Product is available at the following Web site:

http://www.roche.com/policy_continued_access_to_investigational_medicines.pdf.

4.4 CONCOMITANT THERAPY

4.4.1 Permitted Therapy

Concomitant therapy includes any prescription medication, over-the-counter preparations, herbal or homeopathic remedies, and nutritional supplements used by a patient from 7 days prior to the screening visit through to Study Drug Discontinuation Visit. All concomitant medications should be reported to the investigator and recorded on the Concomitant Medications electronic Case Report Form (eCRF).

Patients who experience toxicities should be treated symptomatically as clinically indicated. Patients treated with anti-seizure medications should have levels monitored regularly.

Patients who require maintenance therapy as specified in the eligibility criteria (see Sections 4.1.1 and 4.1.2) should continue to receive maintenance therapy.

Anti-emetics and anti-diarrheal medications should not be administered prophylactically before initial treatment with study drug. At the discretion of the investigator, prophylactic anti-emetic and anti-diarrheal medication(s) may be used as per standard clinical practice before subsequent doses of study drug.

Pain medications administered per standard clinical practice are acceptable while the patient is enrolled in the study.

4.4.2 Prohibited Therapy

Use of the following concomitant therapies is prohibited for at least 7 days prior to Cycle 1, Day 1 dosing (unless a longer washout is required as outlined in the exclusion criteria in Section 4.1.2) and during the study treatment *unless otherwise specified below*:

- Therapy intended for the treatment of cancer (regulatory-approved or experimental), including chemotherapy, radiation therapy, immunotherapy, biologic therapy, herbal therapy, radiopharmaceutical therapy, or endocrine therapy.

Until approximately the end of August 2018, local radiotherapy is not permitted. It is understood that there may be extreme circumstances requiring local radiotherapy in which the investigator does not believe that the symptoms are a result of disease progression (e.g., impending fracture) and the radiation field does not encompass a target/non-target lesion. In such cases, the investigator must obtain approval from the Medical Monitor, and such patients should have a tumor assessment of the lesion(s) before they actually receive the radiotherapy. If a patient received radiation therapy and a target or non-target lesion is included in the field of radiation, the lesion(s) will become unevaluable for tumor response.

Further reasons for avoiding local radiotherapy include the difficulty in distinguishing new symptomatic pain or worsening of lytic bone lesions from disease progression. Radiation therapy to a specific site renders that lesion unevaluable for tumor response. Few clinical data are available about potential toxicities of radiation and treatment with tasisib. Previous clinical experience also suggests that new bone pain is frequently a symptom of disease progression. Bone pain secondary to fulvestrant treatment can be treated with pain medications, nonsteroidal anti-inflammatory drugs (NSAIDs), or corticosteroids.

After approximately the end of August 2018, local radiotherapy is permitted at the discretion of the investigator. Disease progression should be ruled out as tasisib/placebo and fulvestrant must be permanently discontinued for disease progression. It is recommended to hold tasisib/placebo for the duration of the local radiotherapy.

- *Until approximately the end of August 2018, initiation of bisphosphonate or denosumab therapy or modification of the pre-study bisphosphonate or denosumab treatment regimen (e.g., for bone metastasis) should be strongly avoided. Such actions would require the approval of the Medical Monitor. After approximately the end of August 2018, initiation of bisphosphonate or denosumab therapy or modification of the pre-study bisphosphonate or denosumab treatment regimen (e.g., for bone metastasis) is permitted at the discretion of the investigator.*

- *Until approximately the end of August 2018, hematopoietic growth factors (e.g., erythropoietins, G-CSF, and GM-CSF) are not to be administered prophylactically. Use of these agents should be reserved for cases of severe neutropenia and anemia per the labeling of these agents and require the approval of the Medical Monitor. After approximately the end of August 2018, prophylactic administration of hematopoietic growth factors (e.g., erythropoietins, G-CSF, and GM-CSF) is permitted at the discretion of the investigator.*
- Hormone replacement therapy, topical estrogens (including any intra-vaginal preparations), megestrol acetate and selective ER modulators (e.g., raloxifene) are prohibited *unless required to treat adverse events.*

In vitro data with taselisib indicate that it is a substrate of CYP3A4, and results of a clinical study with a potent CYP3A4 inhibitor (itraconazole) suggest that there is a moderate potential for a drug-drug interaction between taselisib and any medication that strongly inhibits CYP3A4. Therefore, the concomitant use of strong CYP3A4 inhibitors including but not limited to ketoconazole, itraconazole, clarithromycin, atazanavir, telithromycin, ritonavir, indinavir, and voriconazole, should be avoided. Caution should be exercised when moderate CYP3A4 inhibitors, including but not limited to fluconazole, ciprofloxacin, cyclosporine, and verapamil are co-administered with taselisib.

On the basis of findings from a clinical study with a potent CYP3A4 inducer (rifampicin), there is a low potential for a drug-drug interaction when taselisib is co-administered with a strong CYP3A4 inducer. Therefore, caution should be exercised when strong CYP3A4 inducers, including but not limited to St John's wort, phenytoin, carbamazepine, rifampicin, rifabutin, and phenobarbital are co-administered with taselisib.

The above lists of medications are not necessarily comprehensive. Thus, the investigator should consult the prescribing information for any concomitant medication when determining whether a certain medication strongly induces or moderately inhibits CYP3A4.

In addition, the investigator should contact the Medical Monitor if questions arise regarding medications not listed above.

Food to Avoid

Grapefruit or grapefruit juice (strong CYP3A4 inhibitor) should be avoided during the study and for at least 7 days prior to Cycle 1 Day 1 of study treatment.

4.5 STUDY ASSESSMENTS

See [Appendix 1](#) and [Appendix 2](#) for the schedule of assessments performed during the study.

4.5.1 Informed Consent Forms and Screening Log

Written informed consent for participation in the study must be obtained before performing any study-specific screening tests or evaluations. Prior to signing the main

consent form for the study, patients may specifically allow for the collection and testing of archival tumor tissue or fresh tumor tissue (e.g., biopsy of a new metastatic lesion) by signing the prescreening consent form. Informed Consent Forms for enrolled patients and for patients who are not subsequently enrolled will be maintained at the study site.

All screening evaluations must be completed and reviewed to confirm that patients meet all eligibility criteria before randomization. The investigator will maintain a screening log to record details of all patients screened and to confirm eligibility or record reasons for screening failure, as applicable.

4.5.2 Medical History and Demographic Data

Medical history includes clinically significant diseases that have occurred within the previous 5 years before Cycle 1, Day 1, breast cancer history (including tumor characteristics such as hormone receptor status, prior cancer therapies, surgeries, and procedures), smoking history, and all medications (e.g., prescription drugs, over-the-counter drugs, herbal or homeopathic remedies, nutritional supplements) used by the patient within 7 days prior to the screening visit.

Demographic data will include age, sex, and self-reported race/ethnicity in accordance with the applicable laws (e.g., health authority requirements).

4.5.3 Physical Examinations

A complete physical examination should include measurement of height (at screening visit only) and weight; an evaluation of the head, eyes, ears, nose, and throat; and an evaluation of the cardiovascular, dermatological, musculoskeletal, respiratory, gastrointestinal, genitourinary, and neurological systems. Any abnormality identified at baseline should be recorded on the General Medical History and Baseline Conditions eCRF.

Until approximately the end of August 2018, an assessment of the patient's ECOG Performance Status (see [Appendix 4](#)) will be completed at screening and as specified in the schedule of assessments (see [Appendix 1](#)).

At subsequent visits (or as clinically indicated), limited, symptom-directed physical examinations should be performed. Particular attention should be given to symptoms related to adverse events of special interest (e.g., diarrhea, colitis, pneumonitis). Changes from baseline abnormalities should be recorded in patient notes. New or worsened clinically significant abnormalities should be recorded as adverse events on the Adverse Event eCRF.

Until approximately the end of August 2018, as part of tumor assessments, physical examinations should also include the evaluation of the presence and degree of enlarged lymph nodes, hepatomegaly, and splenomegaly. After approximately the end of August 2018, as part of tumor assessments, evaluation of the presence and degree of

enlarged lymph nodes, hepatomegaly, and splenomegaly by physical examination should be included per local standard of care.

4.5.4 Vital Signs

Vital signs, collected at screening and at each subsequent visit, will include measurements of respiratory rate, pulse rate, and systolic and diastolic blood pressures (while the patient is in a seated position), temperature, and pulse oximetry for oxygen saturation measurement.

4.5.5 Tumor and Response Evaluations

All known sites of disease must be documented at screening (within 28 days prior to Cycle 1, Day 1) and, *until approximately the end of August 2018*, re-assessed at each subsequent tumor evaluation (every 8 weeks \pm 5 days from the date of randomization). *After approximately the end of August 2018, subsequent tumor evaluations may be conducted per local standard of care.*

Screening assessments must include CT scans of the chest, abdomen, and pelvis; CT scans of the neck and brain imaging should be included if clinically indicated. A documented standard-of-care tumor assessment performed within 28 days prior to Cycle 1, Day 1 may be used for the screening assessment provided it meets the above requirements. Tumor assessments should be performed on this schedule regardless of dose delay or early discontinuation until disease progression.

*Until approximately the end of August 2018, response assessment will be made by the investigator on the basis of physical examinations, CT scans, or MRI, and/or bone scans using criteria outlined in RECIST v1.1 ([Appendix 6](#)). The same radiographic procedure used to assess disease sites at screening should be used throughout the study (e.g., the same contrast protocol for CT scans). Assessments should be performed by the same evaluator to ensure internal consistency across visits. *After approximately the end of August 2018, subsequent tumor evaluations may be conducted per local standard of care.**

*Until approximately the end of August 2018, CT scans throughout the study should include chest, abdomen, and pelvic scans. CT scans of the neck and brain imaging should be included if clinically indicated. At the investigator's discretion, CT scans may be repeated at any time if progressive disease is suspected. *After approximately the end of August 2018, subsequent tumor evaluations may be conducted per local standard of care.**

Bone scan, positron emission tomography (PET) scan, or plain films are not considered adequate imaging techniques to measure bone lesions. However, these techniques can be used to confirm the presence or disappearance of bone lesions. The special considerations regarding the measurability of bone lesions are outlined in RECIST v1.1 (see [Appendix 6](#)).

Bone scans and/or skeletal survey should be performed within 28 days prior to Cycle 1, Day 1. Positive areas on bone scans must be assessed by either CT scan with bone windows, MRI, or X-ray prior to randomization. Bone lesions identified at baseline by CT scan, MRI or X-ray should be assessed using the same modality (CT scan, MRI, or X-ray) and following the same schedule for measurable lesions until disease progression, as described above. Additional bone scans or skeletal surveys should be performed if clinically indicated. *Until approximately the end of August 2018, for patients with bone-only disease not visible on CT/MRI scan or X-ray at baseline, additional bone scans should be repeated every 8 weeks (± 5 days) from the date of randomization and when clinically indicated until disease progression. If a bone scan cannot be performed during the course of the study due to for example a Technetium-99m shortage, alternative imaging options should be discussed with the Sponsor (e.g., sodium fluoride [NaF]). After approximately the end of August 2018, subsequent tumor evaluations may be conducted per local standard of care.*

Until approximately the end of August 2018, abnormalities found on subsequent bone scans must also be confirmed by CT scan, MRI scan, or X-ray assessment. After approximately the end of August 2018, subsequent tumor evaluations may be conducted per local standard of care.

If the patient presents with both irradiated and non-irradiated bone lesions, only the non-irradiated lesions should be followed for tumor assessments unless progression is documented after the radiation.

In the absence of measurable disease at baseline, the following will be considered progression among patients with lytic or mixed (lytic+ sclerotic) bone lesions:

- The appearance of one or more new lytic lesions in bone
- The appearance of one or more new lesions outside of bone
- Unequivocal progression of existing bone lesions

Note: Pathologic fracture, new compression fracture, or bone metastases complications will not be considered as evidence of disease progression unless one of the above-mentioned criteria is fulfilled. Patients with symptoms of rapidly progressing disease without radiological (or photographic) evidence will not be considered to have progressed for efficacy analyses. The evaluation of overall lesion response will be performed according to RECIST, v1.1 as described in [Appendix 6](#). For patients with only bone lesions, RECIST, v1.1 will be extended to include the evaluation of overall lesion response, which will be based solely on non-target lesion responses. Specifically, in the absence of new lesions, the overall lesion response at each assessment will be one of the following: CR, SD, unknown, or PD based on non-target lesion responses. Stable disease would include all assessments not qualifying for complete response, progressive disease, or unknown. In the presence of any new lesion, the overall lesion response will be progressive disease.

To ensure a valid comparison of tumor data and uniformity in the assessment of tumor response during the study, the following procedures must be implemented at the study site:

- *Until approximately the end of August 2018, all lesions identified at baseline (target and non-target) will be reassessed using the same method throughout the course of the study. After approximately the end of August 2018, tumor assessments may be conducted per local standard of care.*
- All CT scans and MRIs obtained for all patients enrolled at the center should be reviewed by the local radiologist who, together with the investigator, will determine the local assessment of response and progression. All bone scans obtained from the patient with bone metastases at baseline also should be reviewed similarly.
- *Until the clinical cutoff date for the primary PFS analysis, which was 15 October 2017, all radiologic data (CT scan, MRI and bone scan, etc.) and photos for skin lesions obtained at baseline, during the treatment period, and the follow-up period must be sent to a central imaging vendor contracted by the Sponsor within 2 weeks of imaging for blinded independent central review (BICR). Additional details regarding the BICR will be outlined in a separate charter.*
- Tumor response and progression will be assessed and will be the basis for the efficacy analyses (along with survival information). The main analysis of the trial will be based on the local radiology review results.

Until approximately the end of August 2018, patients who discontinue study treatment for any reason other than disease progression will continue to undergo tumor-response evaluations until progressive disease. Until approximately the end of August 2018, patients who are discontinued from study treatment because of disease progression will be asked to return for a repeat tumor assessment 4-6 weeks after experiencing disease progression.

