Non-measurable tumor lesions encompass small lesions (longest diameter < 10 mm or pathological lymph nodes with short axis ≥ 10 but < 15 mm) as well as truly non-measurable lesions. Lesions considered truly non-measurable include leptomeningeal disease, ascites, pleural or pericardial effusion, inflammatory breast disease, lymphangitic involvement of skin or lung, peritoneal spread, and abdominal mass/abdominal organomegaly identified by physical examination that is not measurable by reproducible imaging techniques.

SPECIAL CONSIDERATIONS REGARDING LESION MEASURABILITY

Bone lesions, cystic lesions, and lesions previously treated with local therapy require particular comment, as outlined below.

Bone Lesions:

- Bone scan, positron emission tomography (PET) scan, or plain films are not considered adequate imaging techniques for measuring bone lesions. However, these techniques can be used to confirm the presence or disappearance of bone lesions.
- Lytic bone lesions or mixed lytic–blastic lesions, with identifiable soft tissue components, that can be evaluated by cross-sectional imaging techniques such as CT or MRI can be considered as measurable lesions if the soft tissue component meets the definition of measurability described above.
- Blastic bone lesions are non-measurable.

Cystic Lesions:

- Lesions that meet the criteria for radiographically defined simple cysts should not be considered as malignant lesions (neither measurable nor non-measurable) since they are, by definition, simple cysts.
- Cystic lesions thought to represent cystic metastases can be considered as measurable lesions, if they meet the definition of measurability described above. However, if non-cystic lesions are present in the same patient, these are preferred for selection as target lesions.

Lesions with Prior Local Treatment:

- Tumor lesions situated in a previously irradiated area, or in an area subjected to other loco-regional therapy, are usually not considered measurable unless there has been demonstrated progression in the lesion. Study protocols should detail the conditions under which such lesions would be considered measurable.

Appendix 6

Response Evaluation Criteria in Solid Tumors, V 1.1 Modified Excerpt from Original Publication (cont.)

Target Lesions: Specifications by Methods of Measurements

- Measurement of Lesions

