4.4.2.1 Overall Objective Response Rate

Overall ORR is defined as a CR or PR as determined by investigator assessment using RECIST v1.1.

The analysis of ORR will only include patients with detectable *PIK3CA*-mutant tumors who have measurable disease per RECIST v1.1 at baseline as a secondary endpoint of the study and will be tested on the basis of a hierarchical testing procedure to preserve the type I error. That is, the ORR analysis will be conducted at the significance level of two-sided 5% at the time that a statistically significant benefit is observed for the investigator-assessed PFS at either the interim efficacy or final PFS analysis.

An estimate of the response rate and its 95% CI will be calculated using the Blyth-Still-Casella method for each treatment arm. Response rates in the treatment arms will be compared using the stratified Mantel-Haenszel test. The CI for the difference in ORRs between the two treatment arms will be determined using the normal approximation to the binomial distribution. To be conservative, patients with no post-baseline tumor assessments or with post-baseline tumor assessments that have overall responses of “not evaluable” will be considered to be non-responders.

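### The bone-only response rule in protocol Section 4.5.5 is not limited to non-measurable disease, so, read literally, bone-only patients with a measurable soft-tissue component count in the ORR denominator but cannot be scored as partial responders

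*Combined protocol and SAP*

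**What the plan says.** Protocol Section 4.5.5 sets a separate response rule for bone-only disease: "For patients with only bone lesions, RECIST, v1.1 will be extended to include the evaluation of overall lesion response". It then fixes the basis of that scoring, "which will be based solely on non-target lesion responses". If there are no new lesions, "the overall lesion response at each assessment will be one of the following: CR, SD, unknown, or PD based on non-target lesion responses". The remaining category is defined as a catch-all: "Stable disease would include all assessments not qualifying for complete response, progressive disease, or unknown". Partial response is therefore not merely unmentioned; anything short of complete response is assigned to stable disease.

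The same section refers bone measurability elsewhere: "The special considerations regarding the measurability of bone lesions are outlined in RECIST v1.1", with a pointer to Appendix 6. That appendix, under its special considerations on lesion measurability, says that lytic or mixed lytic–blastic bone lesions "with identifiable soft tissue components, that can be evaluated by cross-sectional imaging techniques such as CT or MRI can be considered as measurable lesions", provided that the soft-tissue component itself meets the size definition. Its timepoint-response section sends patients with measurable disease at baseline to Table 1, which has rows for partial response. Table 2, non-target lesions only, is kept for patients with nothing but non-measurable disease.

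The ORR analysis (protocol Section 6.4.2.1, SAP Section 4.4.2.1) is confined to patients "who have measurable disease per RECIST v1.1 at baseline". Neither section excludes bone-only patients. A responder is a patient with complete or partial response.

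**The concern.** The two parts of the protocol classify the same patient differently. By Appendix 6, a bone-only patient with a qualifying soft-tissue component has a target lesion and can reach partial response on a 30% decrease in the sum of diameters. By the bone-only rule in Section 4.5.5, the same scan is stable disease. She belongs to the ORR denominator either way.

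Three things are affected:

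- **ORR.** It is tested at two-sided 5% once PFS is significant, and OS is tested only if ORR also succeeds. Patients who cannot count as partial responders dilute the comparison that opens the OS test.
- **DOR.** Only responders with measurable disease are analysed, so a partial response recorded as stable disease drops the patient from this analysis.
- **PFS.** Without a new lesion, progression would rest on the qualitative non-target judgement instead of the measured target rule (a 20% increase and at least 5 mm over nadir). The main analysis uses local review, so different site readings could give different progression dates.

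CBR is little affected, because absence of progression for 24 weeks also counts as clinical benefit.

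**Working it through.** **Passages side by side**, for a bone-only patient with a lytic lesion whose soft-tissue component meets the size definition.

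| Question | Section 4.5.5 bone-only rule | Appendix 6 |
|---|---|---|
| Does it cover her? | Yes: only bone lesions, no further condition | Yes: measurable disease at baseline |
| Lesions scored | Non-target only | Target and non-target (Table 1) |
| 40% shrinkage of the target, no new lesion, non-target lesions not progressing | Stable disease | Partial response |
| In the ORR denominator? | Yes, through baseline measurability | Yes |
| In the ORR numerator? | No | Yes |

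The list of bone progression criteria just before this rule in Section 4.5.5 is expressly limited to patients without measurable disease at baseline. The response rule that follows carries no such limit.

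**Is there a figure to reproduce?** No. The documents give no expected ORR, no ORR power, no number with measurable disease and no number with bone-only disease. What follows is illustration only.

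**Inputs.** From the documents: 480 *PIK3CA*-mutant patients, 2:1 allocation, two-sided 5%. Assumed: 75% measurable, so 0.75 × 480 = 360, or 120 control and 240 taselisib; ORR of 10% vs 20% if partial response can be scored; a share f of the ORR set that is bone-only with a measurable component; the same response rate in those patients as in the others, all responses partial; and every site applying the restrictive reading.

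**Formulae.** Each arm's ORR becomes p(1 − f). The planned comparison is a Mantel-Haenszel test, so the null standard error uses the pooled proportion (stratification ignored here):

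- SE0 = √[p̄(1 − p̄)(1/120 + 1/240)]
- SE1 = √[pC(1 − pC)/120 + pT(1 − pT)/240]
- power = Φ[(pT − pC − 1.96·SE0)/SE1]

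**f = 0.** p̄ = (12 + 48)/360 = 0.1667; SE0 = √(0.1389 × 0.0125) = 0.0417; SE1 = √(0.00075 + 0.00067) = 0.0376; power = Φ[(0.100 − 0.0817)/0.0376] = Φ(0.487) = 68.7%.

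**f = 8%.** pC = 0.092, pT = 0.184, p̄ = 0.1533; SE0 = 0.0403; SE1 = 0.0364; power = Φ[(0.092 − 0.0790)/0.0364] = Φ(0.359) = 64.0%.

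| Share f | ORR control | ORR taselisib | Power |
|---|---|---|---|
| 0 | 10.0% | 20.0% | 68.7% |
| 2% | 9.8% | 19.6% | 67.6% |
| 5% | 9.5% | 19.0% | 65.8% |
| 8% | 9.2% | 18.4% | 64.0% |

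The loss is 1.1, 2.9 and 4.7 points. With an unpooled variance the level is higher (75.7%, falling to 74.7%, 73.2% and 71.6%), but the loss is of the same order (1.0, 2.5 and 4.1 points). For other assumed rates (12% vs 25%, 15% vs 30%) and 288 to 432 measurable patients, the pooled loss at f = 5% is about 2 to 3 points.

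**Progression.** For patients with only non-measurable disease, Appendix 6 ties unequivocal progression loosely to a 73% increase in volume, equivalent to a 20% increase in diameter (1.2³ = 1.73). A 25% increase in diameter is 1.25³ = 1.95, or 95% in volume, which is above that guide.

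**The case against.** The best defence is that context supplies the missing limit. The bone-only sentence sits in a note attached to a list for patients without measurable disease. The sentence before it says that response follows Appendix 6. RECIST needs extending only for patients without target lesions, since Table 1 already handles the rest. Eligibility makes the same split, between measurable disease and non-measurable disease with an evaluable bone lesion. On this reading the rule is a variant of Table 2 and there is no conflict.

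That may well be what the authors meant, but the text does not say so. The limit is attached to the progression list and is absent from the response rule, which names all bone-only patients and presents itself as a special case. A site could reasonably apply either passage.

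Other parts of the defence stand in full. The measurability wording in Appendix 6 is permissive and conditional on size, so only a subset of bone-only patients is involved. Complete response remains open to them. The rule applies equally to both blinded arms.

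A reader might go further in four ways that the documents do not support:

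- **That the SAP itself classes these bone lesions as measurable.** Its ORR section does not mention bone; it relies on measurability per RECIST v1.1, and the explicit wording is in Appendix 6.
- **That partial response was in fact impossible for these patients.** That holds only where a site followed Section 4.5.5 literally.
- **That clear target growth would not count as progression.** The volume guide in Appendix 6 points the other way, although it is an aid to judgement and not a measurement rule.
- **That the result favours taselisib or inflates type I error.** Equal handling under blinding dilutes ORR and its difference in both arms.

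**Conclusion.** There is a real inconsistency in the text, and it is minor. Taken literally, Section 4.5.5 denies partial response to a subset of patients whom Appendix 6 makes measurable and whom the ORR definition counts.

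The consequence is a probably small dilution of ORR, possible loss of some patients from DOR, and site-dependent progression calls in the same subset. Its size cannot be determined from the documents. The illustrated power loss of 1.1 to 4.7 points rests on an assumed affected share of 2% to 8%, an assumed 75% measurable, assumed response rates, all responses partial, and every site using the restrictive reading; mixed practice would make it smaller. No effect on PFS can be quantified. The point deserves correction mainly because ORR gates OS and the remedy is cheap.

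**What to change.** Limit the Section 4.5.5 bone-only rule to patients whose bone lesions are all non-measurable, scored as in Appendix 6 Table 2. Add that bone-only patients with a measurable soft-tissue component are scored by Appendix 6 Table 1. This is one sentence.

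A wording change alone will not alter responses already recorded: the current protocol post-dates the January 2018 primary PFS analysis, and ORR is tested once PFS is significant. For existing data, therefore, list the bone-only patients with a measurable component by arm, state how each was scored, and report ORR with them scored by Table 1.

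Target measurements may be missing where sites followed Section 4.5.5, because Appendix 6 does not require non-target lesions to be measured. Images were to be sent for central review up to the 15 October 2017 cutoff, so re-measurement should be possible. The cost is a patient listing, some re-reading of images and one supplementary ORR analysis.
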